Study Title: An Integrative Technology Approach to Home-based
Conjoint Therapy for PTSD

Study Identifier: NCT02720016

Document Date: 9/28/21

Study Protocol

Research Design and Methods

Study Design Overview: The primary aim of this 4-year RCT is to evaluate the superiority of CBCT delivered via two modalities (i.e., office-based [CBCT-OB] and home-based via CBT [CBCT-HB]) compared to a clinic-based PTSD Family Education (PFE) control condition on clinical efficacy (PTSD symptoms, relationship quality, functional impairment) and process outcomes (Figure 1). Participating couple (N = 137 dyads) at a US Department of Veterans' Affairs (VA)-based clinical site were randomly assigned to one of three treatment arms (CBCT-OB, CBCT-HB, or PFE-OB) and assessed at five time points: pre-treatment, mid-treatment, post-treatment, 3-months post-treatment, and 6-months post-treatment.

The primary analyses are pairwise comparisons of each CBCT modality with the control condition: CBCT-OB vs. PFE control and CBCT-HB vs. PFE control (Stage 1 analyses in Figure 1). These comparisons are considered primary in the sense that establishing superiority of each modality to control is a necessary condition before consideration of each modality's relationship to each other. Progression to Stage 2 testing (comparison of the two CBCT modalities) will occur only if Stage 1 analyses show that both modalities are superior to control; progression to Stage 3 (a non-inferiority trial, not part of the current proposal) occurs only if no statistically significant differences are found for Stage 2.

[figure not shown]
The primary hypothesis predicts that CBCT delivered via either (CBCT-OB and CBCT-HB) modality will result in significantly greater reductions of **PTSD symptoms**,

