unable to attend an assessment appointment in person, the assessment(s) were offered over the phone. The mid-treatment assessment (between sessions 4 and 5) consisted of self-report questionnaires that the participants completed prior to their mid-treatment therapy session. Both members of the couple completed a baseline assessment interview designed to gather background information and to screen for psychiatric disorders. The PTSD-positive Veteran completed an additional baseline interview to assess PTSD symptoms and DSM-5 diagnosis via the CAPS-5. Participants were advised that each assessment meeting was approximately 2-3 hours in length. Informed consent for each participant was performed by study staff. All diagnostic assessment procedures were performed by the Independent Evaluator (IE) who is trained to administer the CAPS-5 to fidelity via practice interviews until a minimum interrater reliability rating of 90% is achieved. CAPS-5 fidelity was monitored in an ongoing fashion to prevent drift (see Assessment and Treatment Fidelity Monitoring). Study staff (e.g., IE, research assistants) administered self-report questionnaires to the partner and discussed with the IE about inclusion/exclusion criteria. Study staff alerted the therapist if either member of the couple showed a marked worsening of symptoms (e.g., suicidal ideation) or a score of a 2 or higher on item 9 of the BDI-II at any assessment occasion. To minimize the risk of bias, the IE stayed blinded to participants' study condition throughout the study.

Randomization Procedures: Eligible couples were randomly assigned 1:1:1 to receive CBCT-HB, CBCT-OB, or PFE using a permuted block randomization scheme using an excel file, which required confirmation of eligibility criteria before treatment assignment

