is revealed. The randomization schedule was developed and monitored by [name], the study biostatistician, and randomization was communicated to the Veteran by a study approved RA. Study therapists provided care in all conditions. When multiple therapists were available to provide care for the eligible couple, randomization was carried out separately for each therapist, using blocks of decreasing sizes to maintain an approximate balance in the sample sizes for the three arms. However, if a client was recruited from the Oceanside area, placement with an Oceanside therapist was given priority. Only [name], [name] (study statistician), clients and therapists were aware of condition assignment. Once a couple was randomized, they were entered into the study and were included in the ITT analysis. We took the following steps to minimize contamination between the three arms of the study: (1) couples were instructed not to share intervention materials with family members, friends, or other clinic patients; (2) treating VA providers were informed of their patients' participation in the study, but not their condition; and (3) couples were asked not to disclose their treatment assignment to any other counselors or treating physicians.

Treatment Delivery Modality: CBCT-OB and PFE were delivered in the traditional office-based (OB) format - that is, the PTSD-positive participant, his/her partner, and the therapist met in-person in the therapist's office. OB visits took place at two facilities: (1) the Veterans Medical Research Foundation/HSR&D (VMRF/HSR&D) building in La Jolla, CA and (2) 28 miles from La Jolla at the VA clinic in Oceanside, CA. CBCT-HB Couples randomized to the CBCT-HB condition must have had access to DSL or cable internet service or were provided with a VA tablet installed with Wi-Fi through the VA

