Data reliability checks. Reliability and data reduction issues were addressed using descriptive and inferential statistics. Tests of scale reliability will use the Internal Consistency Method and Cronbach's alpha will be calculated. Cronbach's alpha of 0.80 or greater will be considered evidence of sufficient instrument reliability. As described in Assessment and Treatment Fidelity Monitoring, CAPS reliability will be examined via inter-rater agreement.

Analyses for Efficacy Outcomes (Aim 1):

Statistical approach. Longitudinal trajectories of outcomes from baseline to mid-treatment, post-treatment, 3-month, and 6-month follow-up time points were compared using multivariate, multilevel GLMM, which accommodates a wide range of distributional assumptions, including continuous (e.g., CAPS scores, PCL, CSI, IPF, BDI-II, STAXI), categorical/dichotomous (e.g., diagnostic status, treatment completion), ordinal, and count predictors. For outcomes including both members of dyads (e.g., relationship

[figure not shown]
satisfaction), GLMM allowed for modeling multilevel data, as well as for testing other possible cluster effects due to correlation between participants within therapists through inclusion of random effects in the model.

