Model construction. The primary efficacy outcome variables are (1) Veteran-reported PTSD symptom reduction (CAPS severity scores), (2) Veteran- and partner-reported relationship distress (CSI) and (3) Veteran-reported functional impairment (IPF). Secondary variables include PTSD diagnostic status (CAPS), self- reported PTSD symptoms (PCL), depression scores (BDI-II), anger (STAXI-2), and relationship conflict (CTS-2). Variability in scores for each of the primary and secondary outcome measures were examined individually in a series of separate multilevel models. Piecewise/spline models were used to estimate separate slopes for the treatment period and the follow-up period. Each model examined the predictive value of the primary variable of interest: (1) two time slopes (treatment and follow-up; fixed effects), (2) treatment group (fixed effects), and (3) the cross-level interactions of time*treatment group (fixed effects). Baseline scores on the dependent measure were also included as a model covariate, to control for their effect. For couple-based outcomes (e.g., CSI scores), between-dyad, within-dyad, and mixed variables were coded in the model as described by Campbell and Kashy, 2002. As preliminary analyses indicated an imbalance both relationship length and partner-reported CSI scores between treatment groups, subsequent sensitivity models were conducted to control for their effects. For Stage 1 analyses (Aim 1a), pairwise unadjusted and covariate-adjusted differences in least squares means for each outcome variable were compared at mid-treatment, post-treatment, and at the 3- and 6-month follow-up time points using appropriate model

contrasts (i.e., CBCT-OB vs. PFE and CBCT-HB vs. PFE). Next, in Stage 2 analyses (Aim 1b), unadjusted and least squares adjusted means from the GLMM contrast comparisons, along with corresponding 95% CIs, provided estimates of the magnitude (effect sizes), direction, and statistical significance of differences in outcome measures for CBCT-OB compared to CBCT-HB. Progression to a fully powered non-inferiority trial (Stage 3, Figure 1) was determined to occur only if both CBCT delivery modalities are superior to the control intervention (Aim 1a and b). This study provides necessary input information (e.g., variance-covariance and effect size estimates) for the design of the subsequent non-inferiority study.

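### Therapist is a randomisation stratum but is not among the listed model terms, so its place in the CAPS and IPF analyses is not assured and the standard errors of the arm contrasts could be off in either direction.

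*Protocol*

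**What the plan says.** **Design.** The protocol, Randomization Procedures, states that "randomization was carried out separately for each therapist" if more than one therapist could take the couple. Block sizes shrank over time so that the arms stayed roughly equal in number. On who delivered treatment, the same section says: "Study therapists provided care in all conditions". Treatment Providers says that therapists were to treat equal numbers of couples in each condition. Therapist is thus crossed with arm and roughly balanced over arms. Two qualifications apply. The separate lists are conditional on several therapists being available, and couples from the Oceanside area went first to an Oceanside therapist.

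**Analysis.** The SAP, Model construction, states: "Each model examined the predictive value of the primary variable of interest: (1) two time slopes (treatment and follow-up; fixed effects), (2) treatment group". Time-by-group interactions come next in that list. The baseline score is added as a covariate, and sensitivity models add relationship length and partner CSI. Therapist is in none of these lists. It appears once, under Statistical approach, where the GLMM is said to allow "testing other possible cluster effects due to correlation between participants within therapists through inclusion of random effects in the model". That sentence begins with outcomes that involve both members of the couple. The primary outcomes are CAPS, CSI and IPF. CAPS and IPF are reported by the Veteran alone.

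**The concern.** A factor used to restrict the randomisation should normally also be in the analysis. Here the SAP does not say whether a therapist term stays in the primary models, by what rule, or whether it applies to CAPS and IPF. If retention came to depend on a test, that would be a weak basis, because a test of a variance component has little power when therapists are few.

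Two errors are possible if therapist is left out.

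- Balance within therapist removes overall therapist differences from the arm contrast, but a model without therapist leaves that variance in the residual. Standard errors are then too wide and some power is lost.
- If therapists differ in how well they deliver one arm relative to another, that variation does enter the arm contrast, and a model without it understates the standard error.

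The Stage 1 contrasts control entry to Stage 2, since both CBCT modalities must beat PFE, so an error in either direction carries forward.

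**Working it through.** The plan gives no power, effect size, SD, alpha, therapist count or ICC, so there is no figure of its own to reproduce.

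**Inputs from the documents.** 137 couples (Study Design Overview), allocated 1:1:1 (Randomization Procedures), so n = 137/3 = 45.67 per arm.

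**Assumptions.** Two-sided 5% test. K = 4 to 10 therapists. Therapist main-effect variance share rt = 0.01 to 0.10. Therapist-by-arm share rta = 0 to 0.05. Total variance 1. Exact balance, with m = n/K couples per therapist per arm. One visit-specific contrast, without baseline adjustment.

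**Formulas.**

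- True variance of an arm difference: V = 2(1 − rt − rta)/n + 2·rta/K.
- Expected variance from a model without therapist: W = 2[(1 − rt − rta) + (rt + rta)(n − m)/(n − 1)]/n.
- SE ratio: r = √(W/V). Actual test size: 2[1 − Φ(1.96 r)].

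**Worked case.** With K = 6, m = 7.61, rt = 0.05 and rta = 0:

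- V = 2(0.95)/45.67 = 0.04161.
- W = 2[0.95 + 0.05 × 38.06/44.67]/45.67 = 0.04347.
- r = 1.022 and the size is 0.045.

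**Main effect only (rta = 0), K = 4 to 10.**

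| rt | SE ratio | Actual size |
|---|---|---|
| 0.01 | 1.004–1.005 | 0.049 |
| 0.05 | 1.020–1.024 | 0.046–0.045 |
| 0.10 | 1.042–1.050 | 0.041–0.040 |

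**Power (main effect only).** Take a contrast that would have 80% power if the wider SE were correct; the 80% is an assumption. With the many-therapist ratio r = 1/√(1 − ICC), power without therapist is Φ(0.8416 r), because the true spread of the estimate is smaller than the model's SE. Power with therapist is Φ(2.8016 r − 1.96).

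| ICC | r | Without | With | Gain (points) |
|---|---|---|---|---|
| 0.02 | 1.010 | 80.2% | 80.8% | 0.5 |
| 0.05 | 1.026 | 80.6% | 82.0% | 1.4 |
| 0.10 | 1.054 | 81.2% | 84.0% | 2.7 |

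Gains are taken before rounding. The many-therapist ratio slightly overstates the effect when K is 4 to 10.

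**With therapist-by-arm variation (K = 6, rt = 0.05).**

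| rta | SE ratio | Type I error |
|---|---|---|
| 0.01 | 0.988 | 0.053 |
| 0.02 | 0.956 | 0.061 |
| 0.05 | 0.877 | 0.086 |

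Setting W = V gives the share at which the sign changes: rta = rt(1 − 1/K)/(m − 1) = 0.05 × 0.833/6.61 = 0.0063. At rta = 0.05, over all K and rt considered, the ratio runs from 0.81 to 0.96 and type I error from 0.061 to 0.113.

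**Simulation check.** K = 6, 46 per arm, rt = 0.05, 20,000 runs per case. Without therapist, type I error was 0.042, 0.062 and 0.084 at rta = 0, 0.02 and 0.05. With an additive therapist term it was 0.047, 0.069 and 0.095. The additive term repairs the first case but not the other two, where it makes matters slightly worse.

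**The case against.** The strongest reply is that the SAP does provide for therapist. The sentence under Statistical approach speaks of including random effects, and no rule for dropping a term is written anywhere. The list in Model construction is labelled as fixed effects and names no random effects at all, not even one for subject or couple, so silence on therapist there is weak evidence of omission. A figure breaks the sentence that mentions therapist, and its reference to participants within therapists is general. This largely stands. A reader might infer that therapist is definitely omitted, or kept only if significant; the documents support neither. What remains is that they do not commit to including it, least of all for CAPS and IPF.

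A second reply is that the effect is small. Baseline adjustment absorbs some differences in case mix, and a therapist effect that is constant over time largely cancels from the time-by-group slopes. That also stands for the slopes. But the Stage 1 comparisons are differences in least squares means at each visit, where such an effect does not cancel, and therapist influence through treatment arises only after baseline.

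A third reply is that the stratification was conditional and the balance only approximate, with Oceanside priority. This qualifies the exact figures but does not remove therapist as a design factor.

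**Conclusion.** The point holds as a gap in the specification. Couples were randomised within therapist when several were available, and the SAP does not commit to analysing by therapist.

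A reader might infer that the standard errors are simply too wide and the tests conservative. The documents do not support that as a general statement. It is true only if therapists differ in overall outcome and hardly at all in their arm effect. Then the excess is 0.4% to 5%, the test size about 4.9% to 4.0%, and the power gain from modelling about 0.5 to 2.7 points. With 6 therapists and a main-effect share of 0.05, a therapist-by-arm share above about 0.006 reverses the sign, and at 0.02 type I error is about 0.06. Because therapists delivered two different treatments, one of them by two routes, such variation is plausible, but nothing in the documents measures it.

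All sizes rest on the assumed variance shares, therapist counts and exact balance. Confidence is high in the gap and low in the direction of the error. The remedy is cheap enough to be worth making.

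**What to change.** 1. In the SAP, Model construction, include therapist in every primary and secondary efficacy model (CAPS, CSI, IPF and the rest) whatever a test shows. Use a fixed effect if therapists are few and a random intercept otherwise.
2. Under Statistical approach, replace the wording about testing therapist cluster effects with a reference to that term, and say that it covers Veteran-only as well as couple outcomes.
3. Add a sensitivity analysis with a therapist-by-arm random effect, since the additive term does not protect against that variation. With few therapists this component will be poorly estimated, so it belongs in a sensitivity analysis.
4. Report the number of therapists and the therapist ICC for each primary outcome.

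The cost is SAP wording, a few degrees of freedom if therapist is fixed, and one extra sensitivity model. No new data should be needed, because randomisation within therapist requires the therapist to be known.

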Study Title: An Integrative Technology Approach to Home-based
Conjoint Therapy for PTSD

Study Identifier: NCT02720016

Document Date: 9/28/21

Statistical Analysis Plan

Analytic Considerations:

a) Analysis sets. The primary analyses use the ITT sample, which consists of all participants who were randomized. Couples that terminated treatment early were invited to complete follow-up assessments and their data were included in the ITT analyses.

b) Treatment of missing data. Missing data were imputed using multiple imputation procedures in the Blimp software, which uses fully Bayesian model-based specification. In order to explore potential reasons for data missingness, dichotomous treatment status (i.e., non-completion versus completion) was modeled using logistic regression and all subject-level characteristics predicting the retention outcome were included as auxiliary variables in the imputation model.

c) Adjustment for multiple outcomes. To address possible Type I errors due to multiple dependent variables, we specified a priori the primary measures corresponding to the stated a priori hypotheses within the following specified domains: PTSD symptoms, relationship satisfaction and functional impairment. For secondary analyses using additional outcome variables within a given domain, we will report both unadjusted p-values and adjusted p-values using a Tukey-type correction for multiple outcomes. Secondary outcomes and exploratory analyses will be evaluated qualitatively in terms of consistency with primary results and conservatively in terms of statistical significance of results. Sensitivity of study results to adjustment for multiplicity of outcomes will be evaluated.

Preliminary Analyses: All statistical procedures were conducted using SPSS and R software programs. Preliminary analyses examined distributional characteristics of study variables to provide a description of the study sample and to allow for assessment of randomization. Demographic, baseline clinical characteristics of the individual Veteran and/or couple dyad, and other putative prognostic variables (e.g., relationship characteristics) were compared for imbalance across the treatment groups using analysis of variance for continuous variables and chi-square tests for categorical variables. Where, despite randomization, significant group differences at baseline were identified, those variables were included as covariates in sensitivity analyses.

Data reliability checks. Reliability and data reduction issues were addressed using descriptive and inferential statistics. Tests of scale reliability will use the Internal Consistency Method and Cronbach's alpha will be calculated. Cronbach's alpha of 0.80 or greater will be considered evidence of sufficient instrument reliability. As described in Assessment and Treatment Fidelity Monitoring, CAPS reliability will be examined via inter-rater agreement.

Analyses for Efficacy Outcomes (Aim 1):

Statistical approach. Longitudinal trajectories of outcomes from baseline to mid-treatment, post-treatment, 3-month, and 6-month follow-up time points were compared using multivariate, multilevel GLMM, which accommodates a wide range of distributional assumptions, including continuous (e.g., CAPS scores, PCL, CSI, IPF, BDI-II, STAXI), categorical/dichotomous (e.g., diagnostic status, treatment completion), ordinal, and count predictors. For outcomes including both members of dyads (e.g., relationship

[figure not shown]
satisfaction), GLMM allowed for modeling multilevel data, as well as for testing other possible cluster effects due to correlation between participants within therapists through inclusion of random effects in the model.

Model construction. The primary efficacy outcome variables are (1) Veteran-reported PTSD symptom reduction (CAPS severity scores), (2) Veteran- and partner-reported relationship distress (CSI) and (3) Veteran-reported functional impairment (IPF). Secondary variables include PTSD diagnostic status (CAPS), self- reported PTSD symptoms (PCL), depression scores (BDI-II), anger (STAXI-2), and relationship conflict (CTS-2). Variability in scores for each of the primary and secondary outcome measures were examined individually in a series of separate multilevel models. Piecewise/spline models were used to estimate separate slopes for the treatment period and the follow-up period. Each model examined the predictive value of the primary variable of interest: (1) two time slopes (treatment and follow-up; fixed effects), (2) treatment group (fixed effects), and (3) the cross-level interactions of time*treatment group (fixed effects). Baseline scores on the dependent measure were also included as a model covariate, to control for their effect. For couple-based outcomes (e.g., CSI scores), between-dyad, within-dyad, and mixed variables were coded in the model as described by Campbell and Kashy, 2002. As preliminary analyses indicated an imbalance both relationship length and partner-reported CSI scores between treatment groups, subsequent sensitivity models were conducted to control for their effects. For Stage 1 analyses (Aim 1a), pairwise unadjusted and covariate-adjusted differences in least squares means for each outcome variable were compared at mid-treatment, post-treatment, and at the 3- and 6-month follow-up time points using appropriate model

contrasts (i.e., CBCT-OB vs. PFE and CBCT-HB vs. PFE). Next, in Stage 2 analyses (Aim 1b), unadjusted and least squares adjusted means from the GLMM contrast comparisons, along with corresponding 95% CIs, provided estimates of the magnitude (effect sizes), direction, and statistical significance of differences in outcome measures for CBCT-OB compared to CBCT-HB. Progression to a fully powered non-inferiority trial (Stage 3, Figure 1) was determined to occur only if both CBCT delivery modalities are superior to the control intervention (Aim 1a and b). This study provides necessary input information (e.g., variance-covariance and effect size estimates) for the design of the subsequent non-inferiority study.

Primary Analyses for Process Outcomes (Aim 2): Measures of treatment process outcomes include treatment satisfaction (as measured by the CSQ), therapeutic alliance (for both participants' and therapists' WAI), safety issues (tracked by clinical team) and general program management issues tracked by the coordinator. Additional measures of feasibility are recruitment (percentage who agree to participate out of number approached), compliance (percentage of session attended, percentage of homework assignments completed), and retention (dropout rate). The GLMM framework (with appropriate link functions for dichotomous, ordinal, categorical, and continuous feasibility outcomes) was used to compare the feasibility outcomes between each of the three treatment conditions at the post-treatment time point.

Figure 1. Study Design Diagram and Hypothesis Testing Algorithm

Reference

Campbell, L., & Kashy, D. A. (2002). Estimating actor, partner, and interaction effects for dyadic data using PROC MIXED and HLM: A user-friendly guide. *Personal Relationships*, 9(3), 327-342. doi: 10.1111/1475-6811.00023

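### Naming the primary measures in advance does not control Type I error across them, and the readable text does not say how Stage 1 superiority is decided

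*SAP*

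**What the plan says.** **Error control.** SAP, Analytic Considerations c), gives advance naming as its answer to multiple outcomes: "To address possible Type I errors due to multiple dependent variables, we specified a priori the primary measures". For secondary analyses it promises unadjusted p-values together with "adjusted p-values using a Tukey-type correction for multiple outcomes". It closes with "Sensitivity of study results to adjustment for multiplicity of outcomes will be evaluated", giving no method, family or consequence, and mentioning outcomes only.

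**What is tested.** SAP, Model construction, names three primary outcomes: CAPS severity, CSI (Veteran and partner) and IPF. Stage 1 uses "pairwise unadjusted and covariate-adjusted differences in least squares means", once for CBCT-OB against PFE and once for CBCT-HB against PFE. On timing, the SAP says that results "for each outcome variable were compared at mid-treatment, post-treatment, and at the 3- and 6-month follow-up time points". The same models estimate slopes by group: "Piecewise/spline models were used to estimate separate slopes for the treatment period and the follow-up period".

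**What is stated about the decision.** Protocol, Study Design Overview, requires both modalities to be superior to PFE before the two are compared in Stage 2. It lists the three outcome domains together in the primary hypothesis.

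**What the readable text does not state.** It gives no Stage 1 alpha or sidedness and no deciding visit. It does not say whether one outcome or all three must be positive. It does not say which estimate decides: the unadjusted or covariate-adjusted least-squares mean difference, or a slope interaction. Figure 1 is captioned as the hypothesis testing algorithm but is not shown in the text available here.

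**The concern.** Advance naming stops an investigator from searching beyond the list. It does nothing about the number of chances within the list. If a positive result on any listed outcome at any listed visit counts, each extra test adds to the chance of a false superiority finding. Nothing in the readable text shares alpha, ranks the outcomes or adjusts the primary p-values.

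Two conclusions are at stake. One is the trial's main statement that a modality is superior to control. The other is entry to Stage 2: if only one modality works, a chance result for the other lets the two be compared although one was not shown to beat PFE. Without a stated rule, a reader cannot tell what evidence stands behind a reported superiority.

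**Working it through.** The documents give no Stage 1 alpha, power, effect size or SD, so there is no planned error rate to reproduce.

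**Inputs from the documents**
- Two Stage 1 contrasts sharing the PFE arm, allocated 1:1:1 (SAP, Model construction; Protocol, Randomization Procedures).
- Three primary outcomes and four post-baseline visits (SAP, Model construction).
- Mid-treatment is self-report only (Protocol, Assessment Administration) and CAPS is an interview (Protocol, Assessment and Treatment Fidelity Monitoring), so CAPS has three usable visits.
- 137 couples, or 137/3 = 45.7 per arm (Protocol, Recruitment, Attrition, and Retention Procedures).

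**Assumptions, not in the documents**
- Two-sided 5% per test, so 2.5% in CBCT's favour.
- Correlation 0.3-0.5 across outcomes and 0.6-0.9 across visits.
- Correlation 0.5 between contrasts: each difference has variance 2σ²/n and the shared arm gives covariance σ²/n.

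**Number of contrasts**
- One visit: 2 × 3 = 6.
- All visits, if CSI and IPF are collected at mid-treatment: 2 × (3 + 4 + 4) = 22. That collection is inferred, because the protocol does not name the mid-treatment questionnaires.
- All visits, if they are not: 2 × (3 + 3 + 3) = 18.

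**Reference values under independence**, 1 − 0.975^k: k = 6 gives 14.1%, k = 18 gives 36.6%, k = 22 gives 42.7%. Correlation lowers these, so multivariate normal z-statistics were simulated with at least 200,000 draws per setting.

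**Any outcome suffices: chance of at least one false result favouring CBCT, neither modality working**

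| Setting | Chance |
|---|---|
| One visit, 6 contrasts | 11-12% |
| All visits, 18 contrasts | 17-26% |
| All visits, 22 contrasts | 18-29% |

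The all-visit rows let visit means vary freely. If the two linear slopes constrain them, the 22-contrast figure is 17-25% with a separate group effect, or 15-21% if the arms also share a baseline-adjusted start.

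**False entry to Stage 2**

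| Rule | Neither modality works | One works and is always detected |
|---|---|---|
| One outcome, one visit | about 0.5% | 2.5% |
| Any outcome, any visit (18 or 22 contrasts, visits free) | about 3-6% | 10-17% |

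Under the two slope structures, the second row becomes 2.4-4.8% and 9-15% for 22 contrasts.

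**All three outcomes required at one fixed visit.** With neither modality working, a false superiority result for at least one modality has probability 0.1-0.3%. In the worst case, where only one outcome is truly null, each modality's error in CBCT's favour is at most 2.5%. No split across outcomes is needed under that rule.

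**Cost of adjusting over six contrasts.** Holm's hardest step is 0.05/6 = 0.0083. The detectable difference at 80% power is approximately (z for α/2 + z for 80%) × √(2/n). With n = 45.7 this gives (1.960 + 0.842) × 0.209 = 0.586 SD at 0.05 and (2.638 + 0.842) × 0.209 = 0.728 SD at 0.0083. The exact noncentral t values are 0.593 and 0.743 SD. None of these allows for baseline adjustment.

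**The case against.** **What stands.** Much of the structure is stated: the arm pairs, the three outcomes and the both-modalities condition. It would be wrong to say that the plan names no outcome or comparison; what is missing is how the outcomes combine and which estimate decides. Figure 1 may hold part of the rule. If neither modality works, the both-modalities condition keeps false entry to Stage 2 near or below 5% even under the loosest reading. The 10-17% figure needs one modality to be effective and always detected. Stage 2 is also largely estimation to inform a later trial, which limits the harm there.

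**Stronger readings that the documents do not support**
- *That Stage 2 was opened improperly.* The SAP says the Stage 2 contrasts "provided estimates of the magnitude (effect sizes), direction, and statistical significance of differences in outcome measures for CBCT-OB compared to CBCT-HB", in the past tense. The SAP mixes tenses throughout, so this does not show that the Stage 1 condition was met, or that it was bypassed.
- *That the covariate-adjusted contrasts contradict the sensitivity label.* Models adding the imbalanced variables are called sensitivity analyses. In Stage 1, covariate-adjusted could mean adjusted for the baseline score, which every model contains.
- *That requiring all three outcomes would usually fail even with a true benefit.* At an assumed 0.59 SD on every outcome in both modalities, entry to Stage 2 at one visit is 41-46% without baseline adjustment. It is 55-67% if baseline and outcome correlate at 0.4-0.5. The documents give no effect size, so no general statement follows.

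**What does not answer the point.** The hypothesis lists the three outcomes together, but no text makes all three the success rule. The both-modalities condition protects Stage 2, not a separate superiority statement for each modality. The promised sensitivity evaluation has no method and does not reach visits or estimates.

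**Conclusion.** The concern holds for the primary measures. The SAP's stated protection does not do what it is offered to do, and the readable text supplies no decision rule that would make it unnecessary. If any one primary outcome is enough, error in CBCT's favour is more than four times the nominal 2.5% at a single visit, and higher again when visits are also open. These sizes rest on an assumed two-sided 5% per test and assumed correlations, and the 22-contrast count rests on inferred mid-treatment data. They describe one possible reading, not what was done. Under a documented all-three rule at one fixed visit, the inflation across outcomes disappears. Figure 1 should be checked before concluding that no rule was written.

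**What to change.** 1. State the Stage 1 rule actually used: the outcomes and how they combine, the visit, the alpha and the deciding estimate. Say whether it was fixed before the data were analysed, and whether, and on which result, Stage 2 was opened. If Figure 1 holds the rule, put it in the text.
2. If a rule documented beforehand fixes one visit and one model, report Holm or resampling-based adjusted p-values for the three outcomes × two contrasts at that visit. This is not needed if the rule requires all three outcomes. Treat other visits, slopes and the imbalance-covariate models as supportive.
3. If no rule was fixed beforehand, report p-values adjusted across all Stage 1 primary contrasts, and label results that do not survive as non-confirmatory. Choosing one visit now could depend on the data, so this is the default.

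The both-modalities condition for Stage 2 needs no alpha split across modalities.

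**Cost.** No new data, only re-reporting. Fewer results can be called confirmatory, and a rule written after the analysis cannot restore that status. Under item 2, the hardest Holm step raises the detectable difference from about 0.59 to 0.74 SD at 45.7 couples per arm, or from 0.66 to 0.83 SD with the projected 110 completers (36.7 per arm), before baseline adjustment. Under item 3 with 22 contrasts, Bonferroni needs p below 0.05/22 = 0.0023. A method using the correlations would need about 0.003-0.006.
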